4. STATISTICAL ANALYSES

For reporting, a synoptic CSR will be reported. Due to this synoptic nature, limited efficacy data will be reported. All safety outcome measures will be reported, in the CSR.

4.1 GENERAL CONSIDERATIONS

4.1.1 Analysis of Study Conduct

The number of patients who enrolled in Part 1 (OLE) and Part 2 (SM) will be tabulated. The number of patients who discontinued early (early discontinuation of OLE treatment or early termination from the study) or completed the study will be tabulated.

Reasons for early discontinuation of treatment or early termination from the study will be listed and summarized. Any eligibility criteria exceptions and other major protocol deviations will also be summarized. The data will also be summarized by origin of the patient (i.e., by original Phase II OLE protocol or Phase III controlled protocol).

Since Part 1 (OLE) of GA28951 was terminated by the Sponsor on 15th February 2022, no patients are expected to reach treatment completion. As a result of this, the end of Part 1 (OLE) of GA28951 is defined from the last dose date in GA28951 on 15th May 2022.

In summary, the following will be summarized for GA28951 Part 1 (OLE):

- Analysis populations
- Patient disposition
- Study treatment completion/discontinuation
- Study completion/discontinuation
- Major protocol deviations
- Exposure

Treatment Labels

For the OLE population, the only treatment arm to be summarized is:

Group	Patients Included
OLE Etrolizumab	Patients in the OLE population who receive at least one dose of etrolizumab in Study GA28951 Part 1 (OLE)

OLE = Open-Label-Extension

Part 1 (OLE) Day 1

OLE Study Day 1 is defined as the day patient has the first receipt of study drug in GA28951 Part 1 (OLE).

Baseline

For patients who were previously enrolled in one of the Phase III studies, baseline is defined as the last available assessment prior to first receipt of study drug in the Induction Phase of the parent studies: GA28948, GA28949, GA28950, GA29102, and GA29103.

For patients who were previously enrolled in the Phase II trial GA27927, baseline is defined as the last available assessment prior to first receipt of study drug in their parent trial ABS4986g.

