Summary tables will be generated for AEs, serious adverse events (SAEs), deaths, AEs leading to discontinuation of study drug, and AESIs. A listing will be generated for AEs, deaths, selected AESIs/specific AEs, and COVID-19 AEs. Pregnancies will be reported as narratives in the study CSR.

Summary tables of AEs will summarize the incidence of treatment-emergent AEs only. Treatment-emergent events are defined as any new AE reported on or after the first dose of OLE study drug or any worsening of an existing condition. Note that worsening of existing conditions include AEs ongoing from the UC parent studies (GA28948, GA28949, GA28950, GA29102, and GA29103). Otherwise, only AEs reported on or after the first dose of OLE study drug are included. If the onset date of the AE is prior to

the day of first dose, the AE will be considered treatment emergent only if the most extreme intensity is greater than the initial intensity (i.e., the intensity for a given AE increases and its end date is on or after the date of the first dose). For all summary tables, the AEs will be sorted by SOC (in decreasing order of overall incidence) and then by preferred term (PT) (in decreasing order of overall incidence).

For OLE etrolizumab treatment, the incidence count for each AE PT will be defined as the number of patients reporting at least one treatment-emergent occurrence of the event (multiple occurrences of the same AE in 1 patient will be counted only once). The proportion of patients with an AE will be calculated as the incidence count divided by the total number of patients in the population. Each table will also present the total number of AEs reported where multiple occurrences of the same AE in an individual are counted separately.

Rate tables will be generated for selected AEs of interest. The rate per 100 patient years and 95% CIs will be summarized by treatment group and will be calculated by:

$$\begin{aligned} & \text{AE Rate (per 100 patient years)} \\ &= \frac{\text{Total number of AEs (in OLE only)}}{\text{Total number of patient years at risk (in OLE only)}} \times 100 \end{aligned}$$

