4.2.3 Additional Safety Assessments

4.2.3.1 Laboratory Data

Selected laboratory parameters for safety reporting will be described further in the OLE population by summarizing the marked abnormalities and shift tables. Marked abnormalities will be identified according to a Sponsor-defined standard, which generally captures post-baseline laboratory values both outside a reference range and achieving a threshold percent change from baseline. Where needed, laboratory values will be linearly transformed to a standard reference range in order to account for intrinsic differences between males and females or measurement differences between laboratory standards.

Laboratory abnormalities and the patient's worst Common Terminology Criteria for Adverse Events (CTCAE) grade during study will be summarized for hematology and serum chemistry parameters, in addition to change from Baseline summaries.

Elevated liver enzyme tests will be summarized by the following upper limit of normal (ULN) categories as these are indicators of severe liver injury:

- ALT or AST>3ULN and total bilirubin>2 ULN as defined by Hy's law
- ALT or AST>3 ULN

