4.2.3.2 Vital Signs

Vital signs will be summarized using summary statistics and change from baseline. The proportion of patients experiencing clinically significant changes relative to baseline will be reported if appropriate.

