4.2.3.3 ECGs

A shift table for the qualitative ECG assessments will be produced, summarizing the Baseline and worst post-baseline results.

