4.2.4 Open-Label Extension Timeframe

For the open-label extension population, the safety reporting timeframe is defined to capture safety information within the OLE treatment period only. It begins at first dose of study drug in Study GA28951 Part 1 (OLE). The end of the time-frame coincides with the last patient's last visit, this includes safety follow-up in Study GA28951 Part 1 (OLE).

All outputs focus only on safety events after first dose in Study GA28951; these can be handled by flagging events that arise during the OLE treatment period in a manner similar to the identification of treatment-emergent AEs.

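### SAP 4.2.3 names no safety baseline, so the value before the first parent-study dose applies by default, and for patients first given etrolizumab in the OLE the lab, vital-sign and ECG change tables include pre-etrolizumab change

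*SAP*

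**What the plan says.** The definition stands in SAP 4.1.1, under General Considerations. For rollovers from the five Phase III parent trials, "baseline is defined as the last available assessment prior to first receipt of study drug in the Induction Phase of the parent studies". For patients from GA27927, "baseline is defined as the last available assessment prior to first receipt of study drug in their parent trial ABS4986g". The same section defines OLE Day 1 as the day of the first OLE dose. The SAP uses that day for the pMCS remission subgroups and for medical history, not as a reference value for safety.

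The change-based safety outputs are in SAP 4.2.3:

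- **Laboratory (4.2.3.1).** Marked abnormalities follow a Sponsor-defined standard, "which generally captures post-baseline laboratory values both outside a reference range and achieving a threshold percent change from baseline". Shift tables and change-from-baseline summaries are added.
- **Vital signs (4.2.3.2).** "Vital signs will be summarized using summary statistics and change from baseline".
- **ECG (4.2.3.3).** A shift table "summarizing the Baseline and worst post-baseline results".

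None of these says which baseline is meant. Results are shown for one pooled group, OLE Etrolizumab (SAP 4.1.1). Protocol 3.1.1.1 states that patients come from placebo, etrolizumab, infliximab or adalimumab, and that for a substantial share the OLE may bring the first etrolizumab dose.

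SAP 4.2.4 says that "the safety reporting timeframe is defined to capture safety information within the OLE treatment period only".

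**The concern.** A single-arm extension has no comparator, so these tables are read mainly through the within-patient reference value. For a patient on etrolizumab since the start of the parent study, the parent baseline is the correct pre-drug value. For a patient whose first etrolizumab dose is in the OLE, it is not: the difference from that baseline combines what happened on placebo or comparator with what happened on etrolizumab. One rule cannot serve both groups.

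The error can run in either direction. A change carried in from the parent study can be counted as an OLE finding, and an abnormality that returns on etrolizumab can go uncounted. A reader of the pooled table could not tell which had happened.

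Incidence of laboratory abnormalities is a named safety outcome (SAP 1.3.2), and SAP 4 commits to reporting all safety outcomes in the CSR. Vital-sign and ECG change are not named outcomes, so less depends on them.

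**Working it through.** The plan gives no figure on this point to reproduce. The check is a reading of how baseline is used, followed by simple interval arithmetic.

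**Which reference applies.** SAP 4.1.2 and 4.1.3.1 to 4.1.3.3 each restate the parent baseline, for demographics and efficacy. SAP 4.2.3 restates nothing, so the general definition in 4.1.1 is the only one available. Protocol 6.3.2 uses the word for laboratory data without defining it, and SAP 1 says that the SAP supersedes the protocol for reporting. The Sponsor-defined standard is not reproduced, and SAP 5 lists no supporting document.

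**What the difference contains.** For any continuous measure:

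OLE value − parent baseline = (OLE entry value − parent baseline) + (OLE value − OLE entry value)

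For a first-exposed patient, the first bracket lies wholly before etrolizumab.

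**Effect on a categorical shift table, first-exposed patient:**

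| Parent baseline | OLE entry | On etrolizumab | Shift from parent baseline | Shift from OLE entry |
|---|---|---|---|---|
| normal | abnormal | abnormal | counted | none |
| abnormal | normal | abnormal | none | counted |

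**Length of the pre-etrolizumab period, GA28948/GA28949 placebo or adalimumab patients.** Inputs are from Protocol 4.1.1. Parent Week 0 is taken as the first parent dose, and visit windows are ignored.

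- No remission at Week 10, or rescue before Week 10: 10 + 2 = 12 to 10 + 4 = 14 weeks
- Remitters outside the VHP countries in GA28949 and Estonia in GA28948: 14 to 14 + 2 = 16 weeks
- Remitters in those countries: 16 to 16 + 2 = 18 weeks
- Overall: 12 to 18 weeks

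**Share of the baseline-to-visit interval that precedes etrolizumab** = pre-etrolizumab weeks ÷ (pre-etrolizumab weeks + OLE week). Protocol Appendix 1 schedules no hematology, chemistry or vital signs at OLE Weeks 4 and 8, so the first scheduled post-dose assessment is Week 12. ECG follows the 48-week schedule.

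| OLE visit | Lower | Upper |
|---|---|---|
| Week 12 (first labs, vital signs) | 12/24 = 50% | 18/30 = 60% |
| Week 48 (first ECG) | 12/60 = 20% | 18/66 = 27% |
| Week 108 (labs, vital signs) | 12/120 = 10% | 18/126 = 14% |

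An early withdrawal visit or, for labs, an unscheduled visit can come sooner.

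**Other parent studies.** Protocol Table 1 gives exit times for GA28950, GA29102 and GA29103. It does not give the week of the last parent dose, the length of the infliximab washout, or whether maintenance-placebo patients had etrolizumab in induction. No interval is calculated for them.

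**Outputs that do not use baseline.** AE incidence, worst CTCAE grade and the ALT/AST/bilirubin ULN categories.

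**The case against.** The strongest reply is that no sentence applies the 4.1.1 baseline to 4.2.3. Where the SAP wants the parent baseline it says so, and SAP 4.2.4 says of OLE safety events that "these can be handled by flagging events that arise during the OLE treatment period". This shows an intent to separate new findings from carried-in ones. But flagging selects events; it supplies no reference value for a percent change or a shift. Protocol 4.4.1 uses parent final-visit results for the first OLE visit but does not call them baseline. The default reading therefore stands, with one real reservation: the Sponsor-defined standard may set its own reference for marked abnormalities.

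It is also fair to say that the tables are descriptive, that the CSR is synoptic, that clinically significant laboratory and vital-sign findings must be reported as AEs (Protocol 5.4.6.4 and 5.4.6.5), and that part of the laboratory outcome (worst grade, ULN categories) is untouched. These points limit the consequence but do not remove it.

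Four stronger readings are tempting and not supported:

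- **That 50% to 60% measures the bias.** It is a share of elapsed time at one visit and falls steadily afterwards. A carried-in change must also persist to an OLE assessment to count.
- **That the AE rule is anchored purely at the first OLE dose, so the SAP flatly contradicts itself.** The rule begins that way: "Treatment-emergent events are defined as any new AE reported on or after the first dose of OLE study drug". For AEs ongoing from a parent study, however, it compares most extreme with initial intensity, and Protocol 5.4.1 lets the most extreme grade reflect the parent period.
- **That GA27927 patients are affected in the same way.** They had already received etrolizumab in GA27927, so the OLE is not their first exposure. The documents do not say whether anyone on placebo in ABS4986g rolled over.
- **That the baseline predates the parent trial itself.** It is the last assessment before the first parent-study dose.

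**Conclusion.** The point holds for one group and one class of output. The group is patients first given etrolizumab in the OLE after placebo or an active comparator. The outputs are laboratory change and shift tables, vital-sign change, the ECG shift table and, unless the Sponsor's standard says otherwise, laboratory marked abnormalities. Followed as written, the SAP does not show change since starting etrolizumab for these patients.

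The size of the distortion is unknown. The pre-etrolizumab interval can be derived only for GA28948/GA28949, and the documents give no count of first-exposed patients. The conclusion rests on reading 4.1.1 as the default for 4.2.3 and on taking parent Week 0 as the first parent dose. For patients on etrolizumab from the start of the parent study, the existing baseline is right. The matter deserves correction before the outputs are produced, because the change is specific and the data already exist.

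**What to change.** In SAP 4.2.3, define the safety baseline for change-based laboratory, vital-sign and ECG outputs as the last value before the patient's first etrolizumab dose in any study. If that dose is in the OLE, this is the OLE Week 0 value or the parent final-visit value that stands in for it. State whether the Sponsor-defined standard for marked abnormalities uses the same reference.

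Add a supplementary table set against the last value before the first OLE dose for all patients, which answers the OLE-only question in SAP 4.2.4. Keep the parent baseline for demographics and efficacy.

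No new data are needed. Vital signs, ECG, hematology and chemistry are all on the Week 0 schedule (Protocol Appendix 1), and subject numbers carry over from the parent studies (SAP 1). The cost is SAP wording, some reprogramming and one extra table set in a synoptic CSR. The main definition needs unblinded parent-arm and dosing data at the time of reporting, which is assumed; the supplementary tables do not.

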4.1.2 Analysis of OLE Treatment

The following demographic and baseline disease characteristics will be summarized for

the OLE population using baseline from the original parent studies. No treatment comparisons will be made since GA28951 is a single-arm open-label study.

For continuous variables, descriptive statistics including n, mean, median, standard deviation, minimum, and maximum will be calculated. For categorical variables, number and percentage in each category will be displayed.

Demography

- Age
- Age Category (≥ 18 to < 40 , ≥ 40 to < 65 , ≥ 65)
- Sex
- Race
- Ethnicity
- Region
- Smoking status history
- Body mass index
- Weight

Disease Characteristics

- Duration of disease (years)
- Duration of disease category (years) (< 3 , ≥ 3 to < 8 , ≥ 8)
- Disease extent (Left-sided colitis, Extensive/Pancolitis, Other)
- MCS score
- MCS score category (MCS ≤ 9 , MCS ≥ 10) (IxRS and Rave)
- Mean Stool Frequency (SF)
- Worst Rectal Bleeding (RB)
- Physician's Global Assessment (PGA)
- pMCS score
- Endoscopic Subscore
- Ulcerative Colitis Patient-Reported Outcomes, Signs and Symptoms (UC-PRO/SS)
– Functional score
- UC-PRO/SS – Bowel score
- UC-PRO/SS – Systemic score
- Inflammatory Bowel Disease Questionnaire (IBDQ) total score
- Extraintestinal Manifestations

- Fecal calprotectin ($\mu\text{g/g}$)
- Fecal calprotectin category ($<250 \mu\text{g/g}$, ≥ 250 to $<500 \mu\text{g/g}$, $\geq 500 \mu\text{g/g}$)
- C-reactive protein (CRP) levels (mg/L)
- CRP category ($\leq 2.87 \text{ mg/L}$, > 2.87 to $\leq 10 \text{ mg/L}$, $> 10 \text{ mg/L}$)

Baseline Treatments

- Use of oral CS at Baseline (yes vs. no) (IxRS and Rave)
- Use of IS at Baseline (yes vs. no) (IxRS and Rave)
- Prior anti-TNF exposure (yes vs. no) (IxRS and Rave)
- Prior anti-TNF History
- Corticosteroid and Immunosuppressant categories
- Prior Corticosteroid (CS) History

The patients with prior anti-TNF exposure at baseline will be further evaluated to include the number of TNFs previously received and status (e.g., primary non-responder, secondary non-responder, Intolerant, etc).

4.1.3 Primary Efficacy Analysis

To evaluate the efficacy of etrolizumab during long-term open-label treatment, efficacy will be summarized within the population of patients who enroll into the Study GA28951. All data available up until the clinical cut-off date (CCOD) will be reported. The endpoints to be summarized are described below. Due to the open-label nature of the study, no treatment comparisons will be made.

Concerning missing data and treatment withdrawal imputation, there will be 3 strategies employed, described below.

Hybrid LOCF

Within this strategy, at each visit only patients who had the possibility of reaching the visit will be considered in the analysis for that specified visit. Patients will be deemed evaluable at a visit if it was possible for them to have reached this visit based on their enrollment date and the date of the closure of Part 1 of the study.

- Patients for whom it is not possible to have reached the visit at the time of the clinical cut off are termed non-evaluable and will not be included in the analysis at that visit.
- For evaluable patients with missing data, Last Observation Carried Forward (LOCF) will be used from their most recent available data.

- For evaluable patients who previously withdrew from treatment, they will be imputed as a non-responder until their maximum hypothetical visit (i.e., the maximum visit that they could have attended if they had remained within the study).
 - For visits after a patient's maximum hypothetical evaluable visit, they will be removed from the analysis.

As Observed

Within this analysis only the available data at each visit will be summarized. No imputation will be performed for missing data or treatment withdrawals.

Non-Responder

Within this strategy, at each visit only patients who had the possibility of reaching the visit will be considered in the analysis for that specified visit. Patients will be deemed evaluable at a visit if it was possible for them to have reached this visit based on their enrollment date and the date of the closure of Part 1 of the study.

- Patients for whom it is not possible to have reached the visit at the time of the clinical cut off are termed non-evaluable and will not be included in the analysis at that visit.
- Evaluable patients with missing data will be set as a non-responder.
- For evaluable patients who previously withdrew from treatment, they will be imputed as a non-responder until their maximum hypothetical visit (i.e., the maximum visit that they could have attended if they had remained within the program).
 - For visits after a patient's maximum hypothetical evaluable visit, they will be removed from the analysis.

Maximum Hypothetical Evaluable Visit

A patient's maximum hypothetical study day (i.e., the maximum visit that they could have attended if they had remained within the study) is calculated as follows:

$$\text{Maximum hypothetical study day} = (15\text{th May } 2022 - \text{Patient's Day 1 OLE enrollment date})$$

For the hybrid LOCF analysis and non-responder analyses, this will impute patients who have withdrawn as non-responders until the 15th May 2022, which was the latest day of dosing reported in the closure of the study announcement. This excludes patients who withdrew from study drug with reason being stated as "study terminated by sponsor" after 15th February 2022, these patients will not be imputed as non-responders and will be considered 'treatment completers' for the efficacy analysis with data included "as observed"

4.1.3.1 Endoscopic Improvement and Remission at Week 108

As endoscopy data is only collected at a common time point of Week 108 during the OLE Study GA28951, the endpoints of endoscopic improvement and remission will be summarized at this time point. These endpoints will be examined overall and also with patients separated by their previous endoscopic improvement status at their latest visit prior to OLE (e.g., at Week 10/14 or Week 54/62/66 in their parent study).

Population: All patients who enrolled into Part 1 of the OLE Study GA28951.

Baseline: The original baseline value from the parent study will be used.

Sub-groups:

- Table outputs: All patients overall and split by prior endoscopic improvement status and their prior aTNF exposure status.

Analysis 1 - Non-responder

Missing Data:

Patients who are non-evaluable at Week 108 (i.e., it is not possible for them to have reached this visit at the time of the clinical cut-off date) will be removed from the analysis. Patients who remain in Study GA28951 Part 1 (OLE) but are missing endoscopy scores will be imputed as non-responders within the analysis, as LOCF is not appropriate when endoscopy data is not collected routinely.

Intercurrent events: Patients who withdraw during Study GA28951 will be set to non-responders using the composite strategy if they could have reached OLE Week 108 at the time of the clinical cut-off date had they not withdrawn from treatment. This excludes patients who withdrew from study drug with reason being stated as “study terminated by sponsor” after 15th February 2022.

Analysis 2 - As Observed

Intercurrent events: No imputation will be performed for treatment withdrawals

Missing data: If a patient has missing data at a visit, they will be removed from the analysis and no imputation will be performed.

4.1.3.2 MCS Remission at Week 108

As endoscopy data is only collected at a common time point of Week 108 during the OLE Study GA28951, a full MCS score can only be calculated at this visit. Therefore, the endpoint of MCS remission (clinical remission, response?) will be summarized at this time point. These endpoints will be examined overall and also with patients separated by their previous MCS remission status at their latest visit prior to OLE at Week 10/ 14 or Week 54/62/66 in their parent study.

Population: All patients who enrolled into Part 1 of the OLE Study GA28951.

Baseline: The original baseline value from the parent study will be used.

Sub-groups:

- Table outputs: All patients overall and split by prior MCS remission status and their prior aTNF exposure status.

Analysis 1 - Non-responder

Missing Data: Patients who are non-evaluable at Week 108 (i.e., it is not possible for them to have reached this visit at the time of the clinical cut-off date) will be removed from the analysis. Patients who remain in Study GA28951 but are missing MCS scores will be imputed as non-responders within the analysis, as LOCF is not appropriate when endoscopy data, which comprises part of the MCS score, is not collected routinely.

Intercurrent events: Patients who withdraw during Study GA28951 will be set to non-responders using the composite strategy if they could have reached OLE Week 108 at the time of the clinical cut-off date had they not withdrawn from treatment. This excludes patients who withdrew from study drug with reason being stated as “study terminated by sponsor” after 15 February 2022.

Analysis 2 - As Observed

Missing data: No imputation will be performed for missing data

Intercurrent events: No imputation will be performed for treatment withdrawals

4.1.3.3 pMCS Remission

The percentage of patients in remission defined using the pMCS will be summarized for each OLE visit for patients who entered Study GA28951. All OLE visits will be summarized until a minimum of 20 evaluable patients overall remain within the analysis (i.e., an evaluable patient either reached the visit or could have reached the visit if they had remained within the OLE).

Population: Patients who enroll into Part 1 of Study GA28951.

Baseline: The original baseline value from the parent study will be used.

Sub-groups:

- Table outputs: All patients overall, split by aTNF exposure status and by OLE Day 1 pMCS remission status.
- Figure outputs: All patients overall and split by OLE Day 1 pMCS remission status.

Analysis 1 - Hybrid LOCF

Missing data: If patients who remain in Study GA28951 at the specified visit are missing data then LOCF will be used to impute. For visits where patients are non-evaluable (i.e., it is not possible for them to have reached the specified visit at the time of the clinical cut-off date) they will be removed from the analysis.

Intercurrent Events: Using the composite strategy in the case where patients have withdrawn from the Study GA28951, they will be set to non-responders for all visits where they are evaluable. This excludes patients who withdrew from study drug with reason being stated as “study terminated by sponsor” after 15th February 2022.

Analysis 2 - As Observed

Missing data: If a patient has missing data at a visit, they will be removed from the analysis and no imputation will be performed.

Intercurrent events: No imputation will be performed for treatment withdrawals

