GA28948 and GA28949 (cont.)		
 For VHP countries participating in GA28949 and Estonia (participating in GA28948) only: received rescue medication between Week 0 and Week 10, as defined in the GA28948 or GA28949 protocol; patients receiving rescue medication between Weeks 10 and 16 may enroll in Part 1 (OLE) of the OLE-SM study at Week 16
GA28950	
Phase III, randomized, double-blind, placebo-controlled, multicenter study of the efficacy and safety of etrolizumab during induction and maintenance in patients with moderate to severe active ulcerative colitis who have been previously exposed to TNF inhibitors
 
Treatment Arms: etrolizumab, placebo
	
At end of Induction Phase:
 
 Patients who performed the Week 14 visit who did not meet the criteria for clinical response ^b 
During the Maintenance Phase
 
 Patients who met the criteria for clinical relapse ^c Patients receiving rescue medications, as defined in the Study GA28950 protocol 
All remaining patients at the end of Week 66 visit (completion of Maintenance Phase)

GA29102	
Phase III, randomized, double-blind, placebo-controlled, multicenter study to evaluate the efficacy (maintenance of remission) and safety of etrolizumab compared with placebo in patients with moderate to severe active ulcerative colitis who are naive to TNF inhibitors
 
Treatment Arms: etrolizumab, placebo
	
At the end of the Induction Phase:
 
 Patients who performed the Week 10 visit and who have not achieved clinical response ^b at Week 10 Patients receiving rescue medications during the Induction Phase, as defined in the GA29102 protocol 
During the Maintenance Phase:
 
 Patients who met the criteria for clinical relapse ^c Patients receiving rescue medications, as defined in the GA29102 protocol 
All remaining patients at the end of Week 62 visit (completion of Maintenance Phase)

Table 1 Eligibility Criteria for Enrollment into PART 1 of Open-Label Extension and Safety Monitoring Study (GA28951) (cont.)

Protocol Number(s)	Title	Eligibility and Timing for Enrollment ^a

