2. STATISTICAL HYPOTHESES AND SAMPLE SIZE DETERMINATION

2.1 STATISTICAL HYPOTHESES

Due to the non-comparative character of the study, no statistical tests or hypotheses are planned; all efficacy parameters will be summarized descriptively.

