2.2 SAMPLE SIZE DETERMINATION

The maximum number of patients that could have been enrolled in the OLE-SM study is approximately 2100 (i.e., all patients enrolled in the Phase II OLE protocol and the five UC Phase III protocols). No formal sample size calculations were performed.

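### The overall pMCS remission curve rests on a shrinking set of patients whose possible follow-up depends partly on entry route, so it cannot by itself separate change in remission from change in case mix

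*SAP*

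**What the plan says.** SAP 4.1.3.3 plans that "The percentage of patients in remission defined using the pMCS will be summarized for each OLE visit", until fewer than 20 evaluable patients remain. The main analysis is hybrid LOCF, for which SAP 4.1.3 states that "at each visit only patients who had the possibility of reaching the visit will be considered in the analysis for that specified visit". On what decides this, it says: "Patients will be deemed evaluable at a visit if it was possible for them to have reached this visit based on their enrollment date", together with the closure date of Part 1. The maximum hypothetical study day is 15 May 2022 minus the OLE Day 1 date, and a patient is removed at later visits. Patients who withdrew stay in as non-responders up to that limit. The exception is withdrawal after 15 February 2022 because the sponsor ended the study; those data are used as observed.

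pMCS tables are planned overall, by anti-TNF exposure and by OLE Day 1 remission. Figures are planned overall and by OLE Day 1 remission. The summary by origin of the patient in SAP 4.1.1 concerns study conduct. No pMCS output by parent study or entry route is planned, and none for a fixed set of patients.

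Protocol Table 1 sets the time of entry. In GA28950 the early entrants are "Patients who performed the Week 14 visit who did not meet the criteria for clinical response", and all remaining patients enter after Week 66. GA29102 has the same structure at Weeks 10 and 62. In GA29103, patients with disease worsening can enter from Week 10, after washout, and the rest after Week 54.

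**The concern.** Each visit's percentage has its own denominator, and membership depends on how early the patient entered the OLE. In three of the five Phase III parent studies, early entry is a consequence of not responding, relapsing or worsening. If those patients have lower remission in the OLE and make up a larger share of the late visits, the overall percentage falls although remission is constant within every route.

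The Part 1 objective includes long-term efficacy, and pMCS is the only efficacy measure with planned repeated visits; endoscopy and full MCS are summarised at Week 108. There is no comparator. Readers will judge durability from the shape of this curve, and that shape combines the course of remission with a change in who is counted.

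**Working it through.** **No figure to reproduce.** The SAP states that "no statistical tests or hypotheses are planned" and that "No formal sample size calculations were performed". The check is therefore a follow-up calculation from the documents, then an illustration on assumed inputs.

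**Step 1. Possible follow-up by route (documents only).** Possible follow-up = 15 May 2022 − OLE Day 1. For two patients with the same parent start date, the difference equals the difference in entry week.

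| Parent study | Early entry (parent week) | Late entry (parent week) | Gap |
|---|---|---|---|
| GA29102 | 10, induction non-response | 62 | 52 weeks |
| GA28950 | 14, induction non-response | 66 | 52 weeks |
| GA29103 | from 10, worsening | 54 | up to 44 weeks, before washout |
| GA28948/GA28949 | 12, no remission | 14 or 16, remission | 2 or 4 weeks |

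GA27927 patients had their last dose in July 2016 (Protocol Table 1) and start 4 weeks later, or up to 6 with the allowed delay. Day 1 then falls between 29 July and 11 September 2016, which gives about 302 to 296 weeks to 15 May 2022.

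**Step 2. Two-route illustration (assumed inputs).** Parent enrolment is uniform from 2015.0 to an end date of 2018.6, 2019.5 or 2020.0. OLE entry is 10 weeks (early) or 64 weeks (late) after parent start, a gap of 54 weeks, slightly above the 52 in Step 1. The early share p is 40% or 60%. Remission is constant over time, at rE (early) and rL (late) of 20/60, 25/55 or 30/50%.

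Fraction of a route still evaluable at OLE week t: f(t) = (weeks from 2015.0 to 15 May 2022 − entry lag − t) / (weeks in the enrolment window), limited to 0 to 1.

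Overall rate(t) = [p·fE·rE + (1 − p)·fL·rL] / [p·fE + (1 − p)·fL].

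Worked case: window to 2019.5, p = 60%, 25/55. From 2015.0 to closure is about 384.6 weeks and the window is about 234.8 weeks.

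- Week 0: 0.6 × 25 + 0.4 × 55 = 37.0%.
- Week 108: fE = 1, fL = 212.6/234.8 = 0.905. Early share 62.4%, rate 36.3%.
- Week 204: fE = 170.6/234.8 = 0.727, fL = 116.6/234.8 = 0.497. Early share 68.7%, rate 34.4%.
- Week 300: fE = 74.6/234.8 = 0.318, fL = 20.6/234.8 = 0.088. Early share 84.5%, rate 29.7%.

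Over the whole grid the spurious fall is 0 to 2.0 points at Week 108, 1.7 to 3.8 at Week 204 and 4.9 to 12.3 at Week 300. At Week 300, 16% to 28% of patients are still evaluable. Of the enrolment ceiling of about 2100 that is about 340 to 590, so the 20-patient rule would not suppress the visit.

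**Step 3. Sensitivity of the illustration.** A second set of assumptions uses half the patients per route, a 52-week gap, a 208-week window ending 150 weeks before closure, and 30/70% remission. It gives 50.0% at Week 0, 48.9% at Week 108, 42.4% at Week 252 and 30.0% at Week 300, where no late-route patient can be evaluable. With equal rates the curve is flat. With the rates reversed it rises to 57.6% at Week 252. The Step 2 range is therefore not a bound in either direction.

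**Step 4. Adding the omitted sources.** Take the worked case, whose fall at Week 300 is 7.3 points.

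- With 30% or 50% of patients assumed from GA28948/GA28949 (75% of them early, gap 2 weeks), the fall is 5.1 or 3.6 points.
- With instead 5% assumed from GA27927 at 60% remission, all still evaluable at Week 300, it is 2.8 points.
- With both, it is 1.0 or −0.1 points.

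GA27927 patients with Day 1 after mid-August 2016 cannot reach Week 300. When these patients leave, the curve can step down.

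**Step 5. The Day 1 remission split.** On the Step 3 timing, if remission within each Day 1 stratum does not depend on route, both strata are flat (80% and 30%) while the overall curve falls from 52.5% to 37.5% by Week 300. If the routes still differ by 10 points within strata, the strata drift from 78.3% to 70.0% and from 27.3% to 25.0%.

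**Step 6. Fixed cohort.** If everyone counted can reach the last visit shown, route mix is constant. In the worked case the Week 204 cohort is 68.7% early-route throughout and flat at 34.4%.

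**The case against.** The strongest reply is that the SAP already separates much of the case mix. Early entrants are largely defined by non-response, relapse or worsening, and OLE Day 1 remission is a split in both tables and figures. This stands as a real safeguard. It is partial, because non-remitters on Day 1 can include induction failures, relapsers and completers not in remission, and the overall curve is still presented.

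Second, excluding visits that a patient could not have reached is a defensible way to avoid counting administrative closure as failure. That is right, and the rule itself need not change.

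Third, the study is single-arm and descriptive, and SAP section 4 plans a synoptic report with limited efficacy data. No test or error rate is affected; only the reading of the curve is.

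Fourth, the drift is small where most patients are: at most about 2 points at Week 108 in Step 2.

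A reader might infer that late visits must over-represent induction failures and that the curve will therefore fall. The documents do not support this. The over-representation follows only for equal parent start dates. Differences in calendar recruitment between parent studies, or the GA27927 patients, could offset or reverse it.

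**Conclusion.** The point holds as a limit on interpretation. The hybrid-LOCF denominator changes from visit to visit, and in GA28950, GA29102 and GA29103 possible follow-up depends on entry route, by up to 52, 52 and 44 weeks. The overall curve cannot by itself separate loss or maintenance of remission from a change in who is counted. To say that it carries no information on maintenance would go too far, since the Day 1 strata recover part of it.

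The gaps in follow-up come from the documents. The points of drift do not: recruitment dates, route shares and remission by route are all assumed. On the two-route grid the spurious fall is about 0 to 2 points at Week 108, 2 to 4 at Week 204 and up to about 12 at Week 300. With the other parent studies included it can be close to zero at Week 300. The actual direction and size are unknown. That uncertainty is the reason for adding an output that is free of the problem, and the change is a worthwhile low-cost improvement.

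**What to change.** In SAP 4.1.3.3, add the hybrid-LOCF table and figure for two fixed cohorts: patients whose maximum hypothetical visit is at least Week 108, and those for whom it is at least Week 204. Show each from Week 0 to that visit. State that any description of change in remission over time rests on these outputs, and keep the all-evaluable curve as planned. Optionally, tabulate the all-evaluable results by parent study and entry route (induction failure, relapse or worsening, completer, GA27927).

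State also how the cohorts treat patients who withdrew because the sponsor ended the study after 15 February 2022. Their data are as observed, so they could drop out of a fixed denominator. From 15 February to 15 May 2022 is 89 days, about 12.7 weeks, so this should touch about one 12-weekly visit per patient.

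The cost is SAP wording and a few extra outputs from data already held. The fixed cohorts contain fewer patients, and the Week 204 cohort represents earlier entrants rather than everyone enrolled. In the worked case it sits at 34.4%, against 37.0% for all patients at Week 0.
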